5. BACKGROUND AND RATIONALE

Epidemiology:

In the UK heart failure is the biggest cause of hospital admissions in people aged over 65, and is associated with poor morbidity and mortality outcomes if not managed effectively (National Institute for Health Care and Excellence [NICE], 2015). Heart failure is a complex heterogeneous condition characterised by typical symptoms and signs indicative of structural or functional cardiac abnormalities which despite normal filling pressures results in failure to deliver oxygen at a rate proportionate to the demands of metabolizing tissues (Ponikowski et al., 2016). Typical symptoms of heart failure include shortness of breath, reduced exercise tolerance, fatigue, orthopnoea and paroxysmal nocturnal dyspnoea; with signs such as peripheral oedema, functional mitral regurgitation, murmur and elevated jugular venous pressure (Allen et al., 2015). All of these signs and symptoms are however not specific to heart failure and could be caused by alternative conditions which makes diagnosis difficult (Oren and Goldberg, 2017).

Heart failure is categorised based on ejection fraction (EF);

- EF <40% - Heart failure with reduced ejection fraction (HFrEF)
- EF 40-49% - Heart failure with mid-range ejection fraction (HFmrEF)
- EF ≥50% - Heart failure with preserved ejection fraction (HFpEF)

The aetiology of HFpEF is less well understood compared to HFrEF because it is not a uniform disease and patients usually have a combination of morbidities, but there is now a greater focus on it as it is just as prevalent (Lam et al., 2011; Dunlay et al., 2017; van Empel and Rocca, 2018). No effective therapies have as yet been found for management of HFpEF, with therapies that have proven effective in reducing mortality and morbidity in HFrEF patients not having the same effect for HFpEF patients, making this an important research focus (O’Gallagher and Shah, 2018). Approximately half of heart failure patients are now believed to have HFpEF, with the prevalence increasing and set to become the dominant form of heart failure as the condition becomes better understood and diagnosed (Banerjee, 2016; Deaton et al., 2018).

Background:

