HFpEF was previously characterised as ‘diastolic dysfunction’ but this terminology was changed as it was found that diastolic dysfunction was also seen in patients with ‘systolic dysfunction’ (Borlaug and Paulus, 2011). Myocardial stiffness which leads to increased filling pressures is a common pathophysiologic attribute of HFpEF despite its multifactorial aetiology (Telles and Marwick, 2018). Other common conditions associated with HFpEF include: atrial fibrillation (AF), chronotropic incompetence, pulmonary hypertension, right ventricular dysfunction and endothelial dysfunction; with common non-specific risk factors such as: age, gender, hypertension, obesity, diabetes, metabolic syndrome and renal failure (Borlaug, 2014; Ferrari et al., 2015; Harper et al., 2018). This complex heterogeneity of HFpEF which is not yet fully understood highlights the difficulty that clinicians have in being able to diagnose the condition.

Diagnosis of HFpEF is difficult and as of yet there is no test to confirm diagnosis, with current guidelines saying initial diagnosis should include the presence of typical signs and symptoms, an elevated B-type natriuretic peptide (BNP) (>35 pg/mL and/or N-Terminal pro-

B-type Natriuretic Peptide [NT-proBNP] >125 pg/mL) and ejection fraction $\geq 50\%$ (Lekavich et al., 2015; Ponikowski et al., 2016). Echocardiography is the preferred method of assessing for HFpEF due to it being widely available, non-invasive, and able to provide immediate results (Ponikowski et al., 2016). Recent studies comparing the use of echocardiography against 'gold standard' invasive cardiac catheterisation to assess cardiac filling pressures found echocardiography to be just as accurate and reliable (Anderson et al., 2017; Lancellotti et al., 2017). Implications of this research would be that patients could be assessed as outpatients by focus echocardiography rather than invasively in the cardiac catheterisation lab, which would improve patient experience, enhance patient outcomes and prove cost-effective for trusts.

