8.2 Primary and Secondary Outcome Measures

Primary outcome measure

- Accuracy of H2FPEF at predicting HFpEF on the patient population will be assessed as specificity and sensitivity as calculated by logistic regression

Secondary outcome measure

- Investigate if H2FPEF overestimates HFpEF diagnosis on the patient population when compared against known BNP levels.
- To evaluate if H2FPEF can be validated on the patient population and be utilised to improve patient pathway for HFpEF.
- To assess patient outcomes after one year, including any changes in medication or treatment as well as number of hospital admissions and reported symptoms.

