9.3 Eligibility Criteria

Inclusion Criteria

The participant must meet ALL of the following criteria to be considered eligible for the study:

- Age 18-85yrs inclusive
- Currently or previously attended a heart failure clinic with a cardiology consultant at QAH
- Had an echocardiogram, ECG, BNP blood biomarker test in addition to a routine clinical evaluation (including age, weight and number of hypertensive medications) during January 1st 2016 – December 31st 2016.

Exclusion Criteria

The participant may not enter the study if ANY of the following apply:

- Known structural heart disease
- Significant heart valve disease (greater than mild stenosis, greater than moderate regurgitation)
- Pulmonary arterial hypertension
- Constrictive pericarditis
- Pre-existing cardiomyopathy
- Heart transplantation

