11.4 Study Assessments

All data will be collected retrospectively from the heart failure clinic database at QAH. Data will be collected on: weight, number of hypertensive medications prescribed, presence of AF or not, presence of pulmonary hypertension or not, age and filling pressure. These are the factors that make up Reddy et al. (2018) H2FPEF score. In addition the patient's ejection fraction and BNP will also be recorded as a measure to determine HFpEF diagnosis. All data will be anonymised and recorded on a Microsoft Excel spreadsheet, with a separate document documenting the pseudonymised data. All data will have been routinely collected as part of the heart failure patient pathway:

- Echocardiography - A non-invasive ultrasound test which takes approximately 30 minutes and has no radiation risk. Echocardiogram results will be used to ascertain pulmonary pressure and diastolic filling pressure. This will have been performed routinely as part of the heart failure patient pathway at QAH. All scans will have been performed on GE Healthcare Vivid echocardiography machines by a trained sonographer from the Cardiac Investigations Unit at QAH. A standard operating procedure exists for performing echocardiogram. In accordance with local practice personal protective equipment is worn for this test. ECG electrodes and ultrasound gel can be a potential risk to the patient with regards to dermatological reaction/sensitivity, however both are hypoallergenic substances.
- 12-lead electrocardiogram (ECG) - A non-invasive test of the electrical conduction of the heart assessing heart rate and rhythm. ECG results will be used to determine if the patient is in AF or not. All ECG will have been recorded with the use of the hospitals standard machine (MAC 1200, GE Healthcare). All tests will have been

performed by trained staff within the Cardiac Investigations Unit at QAH. Standard operating procedures are followed to perform ECG. ECG will have been performed routinely as part of the heart failure patient pathway at QAH.

- Weight - Using a standard trust scale (Marsden Weighing Company, UK)
- Age and Number of hypertensive medications taken - Assessed from patient records

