13.2 Analysis of Outcome Measures

To determine if the H2FPEF score was accurate in predicting HFpEF the calculated H2FPEF score will be compared against BNP blood test results using the cut-off points stated by the European Society of Cardiology (Ponikowski et al., 2016). To test our hypothesis an analysis of variance test (ANOVA) will be performed to provide one simultaneous evaluation of the data to determine if there is a significant difference between H2FPEF score and diagnosis of HFpEF. A logistic regression analysis will then be carried out to give an odds ratio and provide a predictive analysis of the data. All statistical analysis will be performed using SPSS software.

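### The reference standard leaves out the symptoms and signs that Section 5 makes part of an HFpEF diagnosis, which can understate how far H2FPEF overestimates

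*Combined protocol and SAP*

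**What the plan says.** Section 5 reports current guidance that "initial diagnosis should include the presence of typical signs and symptoms", together with a BNP above 35 pg/mL and/or NT-proBNP above 125 pg/mL, and EF of at least 50%. It also warns of the symptoms and signs it lists: "All of these signs and symptoms are however not specific to heart failure".

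The operative sections say the following.

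- **9.3, eligibility.** Echocardiogram, ECG and BNP test in 2016, "in addition to a routine clinical evaluation (including age, weight and number of hypertensive medications"), and "Currently or previously attended a heart failure clinic with a cardiology consultant at QAH". No symptom or sign is required.
- **11.4, diagnosis.** "the patient's ejection fraction and BNP will also be recorded as a measure to determine HFpEF diagnosis".
- **13.2, analysis.** "the calculated H2FPEF score will be compared against BNP blood test results using the cut-off points stated by the European Society of Cardiology". EF is not mentioned.
- **12.1, form.** Columns for the six score items, the total score and patient outcomes. There is none for baseline symptoms, EF or BNP.
- **13.3.** Collection is limited to data that relate to the score.
- **8.2 and 10.** Symptoms appear only at one year, as part of "number of hospital admissions and reported symptoms".

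The Synopsis states the hypothesis that H2FPEF will overestimate the probability of HFpEF. The primary measure is sensitivity and specificity (Synopsis and 8.2).

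**The concern.** The six score items are common conditions that often occur together, and Section 5 expects over-diagnosis for that reason. The false positives of most interest therefore include patients who have those conditions but not clinical heart failure. If such a patient has EF of at least 50% and a BNP just over the cut-off, the plan counts a true positive.

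For example, an 80-year-old in AF on two anti-hypertensive drugs scores at least 3 + 1 + 1 = 5 of a possible 9 under Section 8.1. With EF 60%, BNP just over 35 pg/mL and no symptoms, that patient is a labelled case, although one of the three parts in Section 5 is missing.

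The error would favour adoption. The Impact part of Section 5 says that if the null hypothesis is accepted, the score will count as validated and could be used at this and other trusts. As no baseline symptom is collected, the study could not show afterwards how many such patients there were.

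**Working it through.** **The plan's own figure.** The Synopsis gives a sample size of 2000 with no prevalence, accuracy target or precision. It cannot be reproduced, and this point does not depend on it.

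**Notation.** As shares of all patients:

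- π: patients who meet all three parts of Section 5
- a: patients without symptoms who are labelled cases on BNP and EF
- se, f, g: score-positive rates in the π group, the a group and the remaining non-cases
- pos = π·se + a·f + (1 − π − a)·g

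The documents give none of these values. They also give no cut-off on the H2FPEF score, so what counts as score-positive is assumed too.

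**Planned definition minus three-part definition:**

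- Excess of score-positives over cases: −a
- False-positive count: −N·a·f
- PPV: +a·f / pos
- Specificity: +a·(f − g) / (1 − π)
- Sensitivity: −a·(se − f) / (π + a)

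The first three point one way whenever a and f are above zero. Specificity is flattered only if f > g. Apparent sensitivity falls if f < se.

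**Illustration 1 (all inputs assumed).** 1000 labelled cases, 150 of them without symptoms, and 1000 non-cases. Score-positive: 80% of the 850, 60% of the 150 and 30% of the 1000. Score-positives = 680 + 90 + 300 = 1070.

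| Measure | As planned | Three-part definition |
|---|---|---|
| Sensitivity | 770/1000 = 77% | 680/850 = 80% |
| Specificity | 700/1000 = 70% | 760/1150 = 66% |
| PPV | 770/1070 = 72% | 680/1070 = 64% |
| Score-positives / cases | 1070/1000 = 1.07 | 1070/850 = 1.26 |

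**Illustration 2, the range over a.** N = 2000 from the Synopsis; assumed π = 0.30, se = 0.80, f = 0.70, g = 0.40.

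| a | False positives, three-part / as planned | PPV, three-part / as planned | Excess in points, three-part / as planned |
|---|---|---|---|
| 2% | 572 / 544 | 0.456 / 0.483 | 22.6 / 20.6 |
| 5% | 590 / 520 | 0.449 / 0.514 | 23.5 / 18.5 |
| 10% | 620 / 480 | 0.436 / 0.564 | 25.0 / 15.0 |
| 20% | 680 / 400 | 0.414 / 0.655 | 28.0 / 8.0 |

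**Specificity at a = 10%, other inputs as in illustration 2.** With f = 0.70 it is 0.557 by the three-part definition and 0.600 as planned. With f = g = 0.40 it is 0.600 both ways. With f = 0.30 it is 0.614 and 0.600, so the planned figure is slightly too low. Sensitivity as planned is 0.775, 0.700 and 0.675 in turn, against 0.800.

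**The case against.** **The setting may supply the symptoms.** The study title places the cohort in a BNP pathway clinic. Sections 9.1 and 9.2 require attendance at a heart failure clinic in 2016, 9.1 specifies a cardiology consultant, and 13.3 requires all tests at the visit. A reader might infer from the words on current or previous attendance in 9.3 that the cohort holds many stable patients at routine follow-up. The documents do not say so, and the 2016 conditions apply as well. The list in 9.3 is also introduced as examples, so the clinical evaluation may have covered symptoms. This part stands: the group without symptoms may be small. But nothing makes symptoms a condition of attendance, and nothing is collected to check it.

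**BNP is an openly declared comparator.** Section 5 is background, and the secondary objective judges overestimation against BNP. That is true, but Sections 11.4 and 13.2 do not agree on the comparator, and the Impact text draws conclusions about HFpEF itself.

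**The primary measures move little.** In illustration 1 specificity and sensitivity shift by 4 and 3 points, and sensitivity looks worse as planned, not better. This stands, and PPV alone would give too strong an impression.

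**Requiring symptoms may add bias.** A reader might conclude that patients without symptoms should be excluded, or always labelled as not having HFpEF. The documents do not support either step. Some may have established disease with controlled symptoms, and an absent record is not an absent symptom. Exclusion also answers a different question: without the 150, illustration 1 gives 980/850 = 1.15, PPV 680/980 = 69% and specificity unchanged at 70%. Since Section 5 calls the symptoms non-specific, the condition may also remove few patients.

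**Conclusion.** The omission is clear from the text: one of the three parts of the diagnosis in Section 5 is neither required nor recorded at baseline. Its direction is known for the hypothesis. If any score-positive patient without symptoms is labelled a case, false positives are undercounted, PPV is too high and the excess of score-positives over cases is too small. For specificity and sensitivity the direction depends on the rates shown above.

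The size is unknown. The PPV gap runs from about 3 points (a = 2%) to 24 points (a = 20%) in illustration 2, and every rate there is assumed. A reader might infer that the plan will hide overestimation. The documents support only that it can understate it. The change is worth making before extraction, because the missing field cannot be reconstructed from the planned data set.

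**What to change.** 1. Add to the Section 12.1 form a baseline field for typical symptoms or signs of heart failure documented at or before the 2016 evaluation (Yes / No / Not recorded), and columns for EF and BNP. Amend 13.3 to allow their collection.
2. State one reference standard, in the same words, in 11.4 and 13.2 and in line with Section 5: documented symptoms or signs, EF of at least 50%, and BNP above the stated cut-off. This also removes the difference between 11.4 and 13.2.
3. Report the EF-plus-BNP definition as a sensitivity analysis. Show the Not recorded group separately and do not treat it as absent.
4. Leave 9.3 as it is on this point, with no exclusion of patients without symptoms.

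The cost is some extra extraction time and incomplete symptom recording. The documents do not say whether the clinic database holds baseline symptoms, although the study already plans to extract reported symptoms at one year. If they cannot be retrieved, state the limitation and its direction, and do not claim on this basis that the score is validated.

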10. SAMPLING

All eligible participants between 01/01/2016 – 31/12/2016 will be included in the study. This is to allow sufficient time to be able to follow patient outcomes up. Outcomes such as any changes to medication and treatment as well as any hospital admissions and reported symptoms will be assessed. Including patients from 2016 will allow us to assess these outcomes one year after their clinic appointment.

11. STUDY PROCEDURES

All data collection will be performed retrospectively. All data will be obtained from the heart failure clinic database. One year follow-up to assess patient outcomes will also be performed retrospectively where data is available.

11.1 Recruitment

Data will be collected retrospectively from eligible participants with data already held on the heart failure clinic database. A member of the patient's direct clinical care team will identify the participants who meet the eligibility criteria for data extraction.

All data obtained will be anonymised with no patient identifiable data being recorded as part of the initial part of the study. A separate pseudonymised document including patient hospital number only will be recorded to allow clinical outcome data to be obtained for the follow-up study.

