2. SYNOPSIS

Study Title	A retrospective observational analysis of a cohort with Heart Failure with Preserved Ejection Fraction from a BNP pathway clinic
Problem statement	Heart failure with preserved ejection fraction (HFpEF) is a complex condition with various causes that is not yet fully understood. Most significantly there is no single method of diagnosing or treating the condition. Recently a novel non-invasive diagnostic criterion to predict the likelihood of HFpEF was proposed by Reddy et al. (2018) called H2FPEF. The main limitation of this study was the use of a single centre population from the Mayo clinic in Rochester, US. Another limitation is that the H2FPEF diagnostic criterion consists of common and often co-existing conditions which could as a result overestimate HFpEF probability. The aim of the investigators is to retrospectively test the H2FPEF criteria on the population at Queen Alexandra Hospital (QAH) in Portsmouth, which is of a lower socio-economic status and greater ethnic diversity. Implications of the project if H2FPEF is proved to be generalizable to the population is that it can be used within the Trust and rolled out to others. This would allow diagnosis to be made quicker and more cost effectively using echocardiography and without the need for invasive cardiac catheterisation. On the other hand if H2FPEF is found not to be applicable to the population then further research would be required to find the ideal diagnostic tool.
Research question / hypothesis	The investigator's hypothesis is that when H2FPEF criteria is compared against retrospectively held data for the patient population at QAH that this will overestimate the probability of HFpEF
Study Design	The study is a single-centre retrospective observational analysis
Study Participants	Patients who attended heart failure clinics at Queen Alexandra Hospital between January 1st 2016 – December 31st 2016
Planned Sample Size	2000
Follow-up duration	1 year
Planned Study Period	04/10/2019 – 30/04/2020
Primary Objective	The primary objective of the investigator's project is to test if the H2FPEF score accurately predicts HFpEF on the population at Queen Alexandra Hospital.

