12. DATA HANDLING AND RECORD KEEPING

12.1 Data Collection Forms

All data will be collected and stored electronically using the following format.

Participant ID	BMI (>30Kg/m ²) Yes/No	≥2 anti-hypertensive medications Yes/No	AF Yes/No	PASP >35mmHg Yes/No	Age (>60 years) Yes/No	E/e' (>9) Yes/No	H2FPEF Score	Patient Outcomes

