14.1 Participant Confidentiality

The study staff will ensure that the participants' anonymity is maintained. Only the relevant clinical data will be collected, and will only be accessed by members of the research team that are involved in the clinical care and would have access anyway. All documents will be stored securely on secured personal hospital drives with password protection and only accessible by study staff and authorised personnel. The study will comply with the Data Protection Act which requires data to be anonymised as soon as it is practical to do so.

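### Eligibility decisions and H2FPEF scoring are not separated from the BNP/EF reference, which leaves the discretionary items (AF status, antihypertensive count, some exclusions) open to bias towards the stated hypothesis

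*Combined protocol and SAP*

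**What the plan says.** **Who selects.** Section 11.1: "A member of the patient's direct clinical care team will identify the participants who meet the eligibility criteria for data extraction". One inclusion criterion in section 9.3 is: "Had an echocardiogram, ECG, BNP blood biomarker test in addition to a routine clinical evaluation". The screener must therefore confirm that a BNP test exists.

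**Who handles the data.** Section 14.1 says that the clinical data "will only be accessed by members of the research team that are involved in the clinical care and would have access anyway".

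**Source and reference.** Sections 11 and 11.4 take all data from the heart failure clinic database. After listing the score items, section 11.4 adds: "In addition the patient's ejection fraction and BNP will also be recorded as a measure to determine HFpEF diagnosis". Under section 13.2, "the calculated H2FPEF score will be compared against BNP blood test results using the cut-off points stated by the European Society of Cardiology".

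**How items are kept.** The form in section 12.1 holds Yes/No answers, for example "≥2 anti-hypertensive medications Yes/No", plus the total score and outcomes. It has no columns for raw values, BNP or EF.

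**Expected result.** The Synopsis hypothesis is that "this will overestimate the probability of HFpEF", and section 5 calls over-diagnosis likely.

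**Safeguards.** Section 8.1 specifies consecutive patients, section 10 includes everyone eligible in 2016, and section 11.2 enters any eligible patient found on screening.

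Sections 11.1, 11.2, 11.4, 12.1 and 12.2 do not mention masking, an order of extraction, a log of exclusion reasons or a second reader.

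**The concern.** In a diagnostic accuracy study the index test should be read without knowledge of the reference. Here the people who may decide eligibility and code the score have access to the BNP and EF that define the reference, and they have said in advance which way they expect the result to go.

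If a doubtful item were coded Yes more readily in reference-negative patients, specificity would fall and the score would appear to overestimate. Excluding low-scoring reference-negative patients under a loosely worded criterion would act in the same direction. Because the form keeps only Yes/No answers, neither could be detected from the study file alone. The result matters beyond the project: the Synopsis and section 5 foresee use of the score in this and other trusts if it is validated.

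**Working it through.** The plan gives no figure to reproduce on this point. The check is a comparison of sections, followed by a conditional illustration.

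**1. Where there is room for discretion**

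| Decision | What the plan fixes | Discretion left |
|---|---|---|
| Age, BMI, PASP, E/e' | Numerical thresholds (8.1) on routine stored measurements (11.4) | Little |
| BNP reference | Laboratory value at guideline cut-offs (13.2) | Little |
| AF, 3 points | 8.1 scores both the paroxysmal and the permanent form; 11.4 uses the ECG to decide whether the patient is in AF | Real: a patient with paroxysmal AF and sinus rhythm on the ECG can be coded either way |
| Antihypertensive count, 1 point | Two or more (8.1), from patient records (11.4) | Some: qualifying drugs are not listed |
| Exclusions for already known structural disease or prior cardiomyopathy | Named in 9.3 | Some: no operational definition |

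**2. Weight of the discretionary items**

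The maximum score in section 8.1 is 2 + 1 + 3 + 1 + 1 + 1 = 9. AF carries 3/9 of it and the drug count 1/9. A patient over 60 on two antihypertensives with no other item scores 1 + 1 = 2 with AF coded No and 2 + 3 = 5 with AF coded Yes.

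The plan states no score cut-off, so all cut-offs from 1 to 9 were tried. For each item, the other five can take 2^5 = 32 patterns. The table gives the number of patterns in which changing the item from No to Yes crosses the cut-off.

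| Cut-off | 1 | 2 | 3 | 4 | 5 | 6 | 7 | 8 | 9 |
|---|---|---|---|---|---|---|---|---|---|
| AF | 1 | 5 | 12 | 19 | 22 | 19 | 12 | 5 | 1 |
| Drug count | 1 | 3 | 4 | 5 | 6 | 5 | 4 | 3 | 1 |

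These count patterns, not patients, because the documents give no item frequencies. They show only that AF is the item most able to change a classification.

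**3. Illustration of size (assumed inputs)**

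From the Synopsis: N = 2000, which has no stated derivation. Assumed: reference prevalence p of 0.3 to 0.7, true specificity Sp of 0.6 or 0.8, and a fraction f of true negatives moved to score-positive.

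- Number of reference-negatives: n = N(1 − p)
- Loss of specificity: Sp × f
- 95% half-width: 1.96 × √(Sp(1 − Sp)/n)

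Example with p = 0.5, Sp = 0.8 and f = 0.05: n = 1000, of whom 800 are true negatives. Moving 40 gives 760/1000 = 0.76, a loss of 0.040. The half-width is 1.96 × √(0.16/1000) = 0.025.

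| f | Loss of specificity | Against half-widths of 0.021 to 0.039 |
|---|---|---|
| 1–2% | 0.006–0.016 | Below in all six scenarios |
| 5% | 0.030–0.040 | Above in four, about equal in one, below in one |
| 10% | 0.060–0.080 | Above in all six |

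Here f is the share of true negatives that cross the cut-off, not the share with a miscoded item. Only some miscoded items would cause a crossing. Nothing in the documents indicates which row, if any, would apply.

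**The case against.** A reader might infer that care-team members score every item in a single pass with BNP, EF and a diagnosis in front of them. The documents do not say that. The sentence in section 11.1 concerns eligibility only. Section 14.1 is a confidentiality clause that limits access, so scoring by care-involved staff is an inference from it. Section 11.4 lists variables without an order. The form in section 12.1 has no BNP or EF column, and no separate clinical diagnosis is planned: HFpEF is to be determined from EF and BNP.

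Other points also count against a strong reading. Four of the six items are threshold readings of measurements made in 2016, before the score's derivation paper of 2018, so the measurements themselves could not have been shaped by this hypothesis. The reference is a laboratory value. Consecutive inclusion of all eligible patients limits selection. Nor would the damage be beyond repair: the separate file of hospital numbers in section 11.1 may allow items to be re-extracted and audited. The AF conflict is partly one of definition, which masking alone would not cure.

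All of this stands, and it narrows the point without removing it. Inclusion of all eligible patients protects only once eligibility has been decided. An objective BNP protects the reference from the score, but not the score from the reference. Anonymisation protects identity and does not mask the person extracting. An audit would mean returning to the source records, which the plan does not provide for.

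**Conclusion.** The plan does not separate eligibility decisions or H2FPEF scoring from the BNP/EF reference, and it should. The exposure is confined to AF status, the antihypertensive count and the undefined exclusions. It is a moderate risk of bias towards the stated hypothesis. It is not evidence that bias has occurred or that the accuracy estimates would be invalid.

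The size cannot be derived from the documents. Under the assumptions shown, moving 1–2% of true negatives across the cut-off would be lost within sampling error, 5% would be about as large as the sampling error or larger in most scenarios, and 10% would exceed it in all of them. The case for acting rests on the low cost of the remedy, not on any one of these figures.

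**What to change.** First, reconcile sections 8.1 and 11.4 on how AF is determined, and write down the rule that extractors will apply. Then set the following order in sections 11.2 and 12.1:

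1. Complete and date each eligibility decision, with a logged reason for every exclusion, before BNP or EF values are extracted.
2. Record the raw value behind each score item (BMI, antihypertensive count, AF finding and its source, PASP, age, E/e') and compute the Yes/No items and the total by formula.
3. Lock and date that sheet.
4. Only then join BNP and EF by participant ID from a second sheet, by bulk export where possible.

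One person can carry out all four steps. The cost is protocol wording, a second worksheet and a second pass through the database. Masking will be incomplete: the screener must still confirm that a BNP test exists and may remember the patient, and if EF stands in the same echocardiogram report as PASP and E/e', it may be seen when those are read. The dated exclusion log and the raw values would at least allow the discretionary decisions to be checked afterwards.
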